Full Title: Efficacy potential of goal management training to improve cognitive

function in older people living with HIV

Abbreviated title: Goal Management training in people living with HIV

Version Number: V1.0

Date of Protocol: April 8, 2016

Funding: Canadian Foundation for AIDS Research (CANFAR)

Principal Investigators: [name] & [name]

Chronic Viral Illness Service of the Royal Victoria Hospital

McGill University Health Centre

Glen site

[name]

Associate investigators: [name]

Neuropsychologist

Professor in the Department of Psychology and Medicine

University of Toronto

Data Management Group: [name]

Royal Victoria Hospital, Room 4.29

[name] The Rotman Research Institute Baycrest Centre for Geriatric Care

[name]

[name]

PROTOCOL SUMMARY

Full Title	Efficacy potential of goal management training to improve cognitive function in older people living with HIV
Short title	Goal Management training in people living with HIV
Sponsor	McGill University Health Centre
Funding	Canadian Foundation for AIDS Research (CANFAR)
Principal Investigators	[name] & [name]
Associate investigators	[name] & [name]
Primary Objectives	Determine the feasibility and acceptability of GMT in people with stable HIV infection who report cognitive concerns
	2. Provide preliminary evidence of the effect of GMT on cognitive performance, compared to a waitlist control group, as measured by (i) cognitive performance tests and (ii) self-report questionnaires
Study Population	 Age ≥ 45 HIV infection for at least 1 year Able to communicate in English or French Capable of providing informed consent Subjective complaints of cognitive difficulties Evidence of cognitive deficit (B-CAM score ≤ 24) Exclusion Criteria Dementia (MSK-rating stage 3 or more-cognitive component only) Concern about capacity to consent Life expectancy of < 3 years or other personal factor limiting the ability to participate in follow-up Non-HIV-related neurological disorder likely to affect cognition Known active CNS opportunistic infection or hepatitis C requiring IFN treatment during the follow-up period Known psychotic disorder Current substance dependence or abuse within the past 12 months.
Study Design	Observational
Sample Size	60
Study Duration	1 year

Contents

PROTOCOL SUMMARY	2
EFFICACY POTENTIAL OF GOAL MANAGEMENT TRAINING TO IMPROVE COGNITIVE FUI	
Background information	

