The proposed project brings together a high profile multidisciplinary team to perform the first randomized controlled study of in-person cognitive training in the HIV population. The core platform is a low burden observational study that aims to understand and address the heterogeneous, multi-factorial nature of compromised brain health in people living with HIV. The pilot project is cost- and time-effective, nested within this ongoing observational cohort study. A standardized intervention will be used, supported by good evidence of efficacy in studies involving other neurological disorders with similar profiles of cognitive impairment. [name] (co-I) had a pivotal role in the validation of the GMT intervention and is an expert in the area of cognitive training. Our team also has extensive experience with all of the project requirements, including HIV clinical trials, large-scale health outcomes research, data management, and advanced statistical methodologies. Addressing or preventing cognitive impairment is a pressing concern for people living with HIV, and those who care for them. Cognitive training is resource consuming and not the standard of care in HIV. High quality evidence is needed to justify committing resources to such training. We propose work that directly addresses this need, taking advantage of the 'window of opportunity' provided by the on-going +BHN project. Regardless of the outcome, this study will provide important information to orient future work aiming to improve cognition in people living with HIV. The results of this pilot study will inform the development of a full randomized controlled trial.

Study Hypothesis

We hypothesize that GMT, a cognitive rehabilitation intervention, will lead to improved cognitive function as assessed by better performance on cognitive tests and reduced cognitive concerns in people with stable HIV infection who report cognitive concerns at baseline, compared to a wait-list group.

Study Objectives

The specific objectives of this study are to:

- 1. Determine the feasibility and acceptability of GMT in people with stable HIV infection who report cognitive concerns
- 2. Provide preliminary evidence of the effect of GMT on cognitive ability, as measured by changes in (i) cognitive performance tests and (ii) self-report questionnaires.

STUDY DESIGN

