This is a concurrently controlled trial. Study participants will be randomly selected from those participating in the ongoing, longitudinal +BHN study at 2 sites in Montreal (The Montreal Chest Institute and L'Actuel Medical Clinic). This CIHR Team Grant-supported observational, prospective cohort study is enrolling consecutive patients attending 5 HIV clinics across Canada for a total sample of 900, followed every 9 months for 27 months. Inclusion criteria are: age 35 y or older, HIV infection for at least 1 year, able to communicate in English or French and capable of providing informed consent. Exclusions are presence of dementia, life expectancy < 3 y, other neurological disorder including active opportunistic CNS infection, psychotic disorder, current substance dependence or abuse, and Hepatitis C requiring interferon therapy during the study period. Montreal sites will enroll 350 participants, which should provide an adequate pool for recruitment to this sub-study.

The GMT intervention will be tested in a randomly selected sub-group (N=30) of this cohort who meet the following additional criteria: over age 45, subjective complaints of cognitive difficulties, and performance on objective computerized cognitive tests that falls at or below the 50th percentile of performance in the cohort as a whole (as measured by the cohort study's primary outcome, a combination of self-report and performance items called the Brief Cognitive Ability Measure [B-CAM] (17)). The concurrent control group will be comprised of those eligible for GMT but not randomly selected.

Procedure

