Participants will be recruited at the time of their routine +BHN study visit, at which comprehensive information about their current health status, function, quality of life, cognitive concerns, and cognitive performance is already being gathered. Following informed consent, all participants will complete a short set of neuropsychological tests and questionnaires that have been shown to be sensitive to the effects of GMT [Sustained Attention to Response Task-SART (18),Tower of London (19), and Dysexecutive Questionnaire-DEX (20)] immediately, or at a visit arranged for this purpose, separate from the +BHN main study. Participants will then begin GMT, as described below. Within 4 weeks of completing the GMT program, they will be asked to repeat the neuropsychological testing and complete additional tests which form part of the standard +BHN visit at a second study visit, coincident with the +BHN study visit if timing permits.

Intervention

The standard GMT program lasts 9 weeks and involves 9 weekly 2-hour small group sessions led by a trained therapist. It follows a manualized program that teaches participants a series of techniques to build attention and executive function, and shows them how to implement these techniques in their everyday life. The small group sessions allow individualization of the training to show how it can be applied to

meet the particular challenges reported by participants, and explicitly encourage participants to share their challenges and successes with others in the group to promote learning and engagement with the program. The sessions are reinforced with homework, in which participants practice what they have learned. Sessions will be audiotaped for later review by the trainer and/or study investigators to ensure adherence to the intervention manual. The material, including homework, is provided in a workbook that participants use throughout the training, and keep for later reference.

TREATMENTS

There are no pharmacological treatments involved in the current study.

STUDY EVALUATIONS/PROCEDURES

Informed Consent

The subject will be asked to read and sign the approved informed consent form prior to any assessments being performed. Sufficient opportunity will be given to discuss the study and consider the information in the consent process prior to agreeing to participate. The original signed informed consent form will be retained in the subject's study files and a copy will be provided to the subject.

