Subject Identification Number Assignment

Subject Identification (ID) numbers assigned for the core platform will be used for this sub-study.

DETAILS OF STATISTICAL ANALYSIS

Analysis and Sample Size

The feasibility and acceptability of the GMT will be evaluated in the whole group (N=30) based on the proportion of GMT sessions attended, the proportion of the homework completed, and the overall level of satisfaction with the program, as determined by an anonymous questionnaire filled out by the participants at the end of the intervention.

The potential impact on cognition of GMT will be evaluated in two ways: (i) a within-person analysis of change in cognitive outcomes after all persons have completed the GMT program; and, for exploratory purposes, (ii) a between group comparison contrasting change in cognitive outcomes between the GMT group and the concurrent control group assessed in the main study.

For all analyses, the B-CAM (performance measure) will be the primary cognitive outcome and a global outcome response will be based on changes in the B-CAM and on four secondary cognitive outcome measures: SART, Tower of London, Dysexecutive Questionnaire-DEX and PDQ.

For the within-person analysis, change from pre-to post will be calculated for each person and a 95% confidence interval (CI) around the mean change will be calculated. A 95% CI that excludes 0 indicates statistically significant change. A sample size of 30 will provide 80% power to detect an average standardized response mean (effect size for change) of 0.38, within the reported range for GMT in other conditions. However, average change is not very interpretable as this average change can occur in many ways including no change for a lot of people and large change for a few, or even deterioration for some. To provide a more interpretable estimate of treatment impact, an overall effect will also be reported, based

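### The only efficacy analysis not labelled exploratory is an uncontrolled pre-post change in people selected for a low B-CAM; it cannot separate GMT from regression to the mean or practice

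*Combined protocol and SAP*

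**What the plan says.** **Aim.** The Study Hypothesis expects improvement "in people with stable HIV infection who report cognitive concerns at baseline, compared to a wait-list group". Objective 2 in the Protocol Summary concerns "the effect of GMT on cognitive performance, compared to a waitlist control group". Objective 2 under Study Objectives names no comparator.

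**Ranking of analyses.** Analysis and Sample Size evaluates GMT's potential impact on cognition in two ways. The first is the mean within-person change with a 95% CI, plus a responder proportion in the same people. The second is introduced as "and, for exploratory purposes, (ii) a between group comparison contrasting change in cognitive outcomes between the GMT group and the concurrent control group". A CI excluding 0 is read as statistically significant change.

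**Selection and outcome.** B-CAM is the primary cognitive outcome for all analyses. It is also an entry filter. The Protocol Summary requires "Evidence of cognitive deficit (B-CAM score ≤ 24"), and Study Design requires "performance on objective computerized cognitive tests that falls at or below the 50th percentile of performance in the cohort as a whole"; B-CAM is the measure used there.

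**Baseline.** People are recruited at a routine +BHN visit. Under Procedure, "Following informed consent, all participants will complete a short set of neuropsychological tests and questionnaires that have been shown to be sensitive" to GMT; these are SART, Tower of London and DEX. No further B-CAM before training is described.

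**Controls.** "The concurrent control group will be comprised of those eligible for GMT but not randomly selected", according to Study Design. The cohort they come from is "followed every 9 months for 27 months".

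**The concern.** A group chosen for low scores on an imperfectly reliable test will, on average, score higher next time. Repeating a cognitive test can also raise scores through practice. A one-group change adds both to any GMT effect and cannot separate them. The controls pass the same B-CAM filter, so at comparable retest intervals both influences should largely cancel in the comparison.

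A controlled comparison is planned and sized; the fault is its rank. The analysis that answers the stated hypothesis is the one marked exploratory, and the analysis placed first can look positive with no GMT effect. The statement that a CI excluding 0 shows change is correct, but nothing warns that such change is not evidence of a GMT effect. The plan's own caution about average change concerns how change is spread across people, not what caused it. The pilot is meant to inform a full randomised trial, so a spurious signal would carry forward.

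**Working it through.** **The plan's own figure.** The plan states 80% power at a standardised response mean (SRM, mean change / SD of change) of 0.38 with n = 30. The detectable SRM is (1.960 + 0.842)/√n.
- n = 54 (the plan's 30 × 1.8): 2.802/7.348 = 0.381, which matches.
- n = 30: 2.802/5.477 = 0.51.

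So 0.38 describes an average over five measures. For B-CAM alone the detectable SRM is 0.51.

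**Regression to the mean.** Inputs from the plan: n = 30, a two-sided 95% CI, and selection at or below the cohort median. Assumptions: bivariate normal scores with cohort SD 1, test-retest correlation r, selection score used as baseline, the same score as outcome, no GMT effect and no practice effect.
- Mean of those selected: −√(2/π) = −0.798; variance 1 − 2/π = 0.363
- Expected gain = (1 − r) × 0.798
- SD of change = √[(1 − r)² × 0.363 + 1 − r²]
- Chance that the CI lies above 0: noncentral t, 29 df, noncentrality SRM × √30

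Worked for r = 0.8: gain 0.2 × 0.798 = 0.160; SD √(0.0145 + 0.36) = 0.612; SRM 0.261; noncentrality 1.43; probability 0.281.

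| r | Gain | SD of change | SRM | P(CI above 0) |
|---|---|---|---|---|
| 0.7 | 0.239 | 0.737 | 0.325 | 0.405 |
| 0.8 | 0.160 | 0.612 | 0.261 | 0.281 |
| 0.9 | 0.080 | 0.440 | 0.181 | 0.159 |
| 0.95 | 0.040 | 0.314 | 0.127 | 0.099 |

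Simulation gives 0.412, 0.278, 0.162 and 0.099. The nominal value is 0.025.

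**Lower subgroup mean.** Eligible people are also older and report complaints, so they may regress to a lower mean. If that mean is 0.5 SD below the cohort median (assumption), 0.798 is replaced by φ(0.5)/Φ(0.5) = 0.509. The SRMs are 0.205, 0.165, 0.115 and 0.081, and the probabilities 0.191, 0.139, 0.089 and 0.063.

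**Fresh baseline.** With a new B-CAM taken after selection, the simulated probability is 0.025 to 0.026. Adding a practice gain of 0.1 cohort SD (assumption) gives SRM = 0.1/√[2(1 − r)] = 0.129, 0.158, 0.224 and probabilities 0.101, 0.131, 0.219 at r = 0.7, 0.8, 0.9.

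**The controlled comparison on B-CAM alone.** For a two-sample t test (two-sided 5%, 80% power), the detectable difference is 0.588 residual SD at 30 v 100. Multiplying by √(1 − r²) = 0.714, 0.600, 0.436 gives 0.42, 0.35, 0.26 cohort SD at r = 0.7, 0.8, 0.9. At 30 v 30 (if the Summary's 60 splits equally, an assumption) it is 0.736 residual SD.

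**Gain from baseline adjustment.** Residual variance falls from SD(change)² to 1 − r². At r = 0.7 that is 0.51 against 0.543, or 6%; at r = 0.8 and 0.9 it is 4% and 2%.

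**Unequal intervals.** If r is 0.9 for the shorter GMT interval and 0.8 for controls (assumption), regression differs by 0.160 − 0.080 = 0.080 cohort SD.

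**The case against.** **The baseline may be fresh.** Random selection against a cohort percentile could use an earlier +BHN visit, with the recruitment visit supplying a new B-CAM. Regression would then largely disappear. This reading is possible and the text does not settle it. Practice gain would remain, though its size is unknown.

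**The 41% is an unfavourable case.** It is. With the eligible group's mean a full 1 SD below the cohort median, the same formulas give 9%, 7%, 5% and 4%. The relation of the cut-off of 24 to the median is also unknown. The direction holds across these cases; the size is uncertain.

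**The selection and outcome scores may differ.** Study Design describes B-CAM as mixing self-report and performance items but refers to computerised tests for selection, and the outcome is described as a performance measure. If the scores differ, the regression effect changes. The figures are conditional on one score.

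**It is a pilot.** Feasibility is objective 1, the objective under Study Objectives fits a within-person analysis, and nothing is formally named the primary analysis. All true. But the hypothesis and the Summary's objective are comparative, and only the comparative analysis is marked exploratory.

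**The comparison has its own weaknesses.** Its retest intervals may differ, although Procedure already aims for a second visit that coincides with +BHN. The plan's 0.4 SD is for all measures together, so it is not directly comparable with 0.588 for B-CAM alone. These points call for care in carrying out the comparison; they do not make the uncontrolled change a better test.

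**Conclusion.** The concern holds. The ranking of analyses does not match the hypothesis, and the analysis placed first cannot attribute change to GMT. That conclusion follows from the design and needs no assumed value of r.

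The size does depend on assumptions. If the selection score is the baseline and the same score is the outcome, the chance of a CI above 0 with no GMT effect is about 10% to 41% for r from 0.95 down to 0.7. It is 6% to 19% if the eligible group's mean is 0.5 SD below the cohort median. With a fresh baseline it is about 2.5% without practice, and 10% to 22% with a practice gain of 0.1 SD. Confidence is high on the ranking and only moderate on any single figure. The plan should be corrected; the feasibility objective is unaffected.

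**What to change.** 1. State which B-CAM assessment is the baseline, and whether the selection and outcome scores are the same.
2. Make B-CAM in GMT versus eligible, not-selected controls the main efficacy analysis, adjusted for baseline B-CAM and analysed as randomly selected. Say how selected people who decline GMT are handled.
3. Report pre-post change as descriptive, and state that a CI excluding 0 shows change, not a GMT effect.
4. Use +BHN B-CAM assessments at comparable intervals. GMT retest can fall about 13 weeks after training starts (nine weekly sessions plus up to 4 weeks), against 9-month control visits. Adjusting for interval works only if the intervals overlap; the next routine +BHN visit in both groups is one option.
5. Reconcile the comparator: wait-list with a sample size of 60 (Protocol Summary), or about 100 eligible, not-selected people (Study Design; Analysis and Sample Size).
6. Restate the detectable B-CAM effect from the working above, for whichever comparator is kept.

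**Cost.** This is mostly SAP wording, because B-CAM is the cohort study's own primary outcome and no new arm or participants are needed. Visit timing and decliners need attention. The stated precision becomes less favourable, and using the routine visit may measure some GMT participants later. If intervals stay unequal, some bias remains. Baseline adjustment adds only a few per cent in precision over change scores.

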on the proportion of individuals who improved at least 0.5 SD on one of the cognitive outcome measures. A change of 0.5 SD is considered clinically relevant (21). For this analysis, generalized estimating equations (GEE) will be utilized to adjust for a possible correlation between the different measures. The outcome will be the binary response for each of the five cognitive outcomes, and the analysis yields an estimated charge proportion adjusted for non-independence. Having five outcome measures increases the number of observations available for analysis by a factor of 1.8, termed the design effect. The design effect (22) is a function of the number of measures (here m-1) and the correlation between measures (estimated at 0.2). Hence the number of observations effectively available for analysis is 30 x 1.8 or 54. With this sample size, the 95% CI will exclude a low responder proportion (20%) as long as the responder proportion is greater than 28% (www.vassarstats.net).

For the between-group analysis, 30 people in the intervention group and a concurrent control group of 100 (with five outcome measures, the effective sample size is inflated by the design effect of 1.8). Thus, using all measures, the sample would provide 80% power to detect an effect size of 0.4 (0.4 of a SD). For this analysis, generalized estimating equations (GEE) for a continuous outcome will be utilized to adjust for a possible correlation between the different measures. Each measure will be transformed onto a 0 to 100 scale for permit a global intervention effect to be estimated.

REFERENCES

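### The exploratory between-group comparison of B-CAM should adjust for baseline B-CAM rather than contrast change alone: a modest gain at almost no cost

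*Combined protocol and SAP*

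**What the plan says.** In the combined protocol and SAP, *Analysis and Sample Size* evaluates the effect on cognition in two ways. The first is a within-person analysis of change. The second, labelled exploratory, is "a between group comparison contrasting change in cognitive outcomes between the GMT group and the concurrent control group assessed in the main study". B-CAM is the primary cognitive outcome in all analyses. SART, Tower of London, DEX and PDQ are secondary.

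For the between-group model, "generalized estimating equations (GEE) for a continuous outcome will be utilized to adjust for a possible correlation between the different measures". On scaling, "Each measure will be transformed onto a 0 to 100 scale". The GEE is there to handle correlation among the five measures. No baseline value or other covariate is named.

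The planned size is "30 people in the intervention group and a concurrent control group of 100". The power statement, which covers all measures together, is that "the sample would provide 80% power to detect an effect size of 0.4 (0.4 of a SD").

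On the availability of baselines:

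- **B-CAM.** *Study Design* admits people at or below the cohort median on the B-CAM, and the Protocol Summary gives a B-CAM cut-off. Controls are the eligible people who were not randomly selected. Both groups therefore have a baseline B-CAM.
- **PDQ.** It is named only in the analysis section. *Procedure* says that cognitive concerns are already recorded at cohort visits, so a baseline in both groups is plausible but not stated.
- **SART, Tower of London, DEX.** *Procedure* describes these for participants who then start GMT. No control data are described.

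**The concern.** An analyst following the text would regress change on group. That fixes the coefficient on baseline at 1, whereas a score measured with error has a slope below 1. Two things follow. Residual variance is larger than it need be. And if the 30 selected people happen to start lower or higher than the controls, regression to the mean turns part of that difference into an apparent effect in the sample at hand.

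This is the plan's only controlled estimate, since the within-person analysis has no comparator. The hypothesis is framed against a control group, and the results are meant to inform a full randomised trial. Avoidable noise in this estimate therefore matters somewhat, even in a pilot.

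**Working it through.** **Inputs.** From *Analysis and Sample Size*: 30 v 100, multiplier 1.8, effect 0.4 SD, power 80%. Two-sided 5% is assumed, by analogy with the 95% CI rule of the within-person analysis. From *Study Design*: baseline B-CAM cut at the cohort median. The baseline-to-follow-up correlation r is not given, and r = 0.5, 0.7, 0.8 is assumed. The only correlation stated is 0.2 between different measures, which is another quantity. Baseline and follow-up are taken as bivariate normal with equal SDs in the cohort.

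**1. The plan's own figure.** With the multiplier the groups are 54 and 180.

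- SE = √(1/54 + 1/180) = 0.155 SD.
- Power at 0.4 = Φ(0.4/0.155 − 1.96) = 73.2%, not 80%.
- The effect detectable with 80% power is (1.96 + 0.842) × 0.155 = 0.435, which rounds to the stated 0.4. The gap is compatible with one-decimal rounding.

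**2. Variance ratio for B-CAM.** Write follow-up as r × baseline + error, with error variance 1 − r². Cutting a normal baseline at its median leaves baseline variance 1 − 2/π = 0.363.

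- Variance of change = (1 − r)² × 0.363 + (1 − r²).
- Residual variance after baseline adjustment = 1 − r².

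| r | Change variance | Adjusted variance | Ratio | Gain in effective people |
|---|---|---|---|---|
| 0.5 | 0.841 | 0.750 | 0.89 | 12% |
| 0.7 | 0.543 | 0.510 | 0.94 | 6% |
| 0.8 | 0.375 | 0.360 | 0.96 | 4% |

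**3. Power for B-CAM alone, 30 v 100.** SE = √(1/30 + 1/100) = 0.208 in units of the SD of change.

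- Change contrast at 0.4: Φ(0.4/0.208 − 1.96) = 48.5%.
- Adjusted: divide the SE by the effect of the ratio, that is, use 0.208 × √ratio. Power becomes about 53%, 51% and 50% for r = 0.5, 0.7 and 0.8.

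**4. Chance imbalance on B-CAM.** The truncated baseline SD is √0.363 = 0.60 cohort SD.

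- SE of the baseline difference = 0.60 × 0.208 = 0.125 cohort SD.
- Given an imbalance D, the change contrast moves by −(1 − r)D.
- At two SEs, D = 0.25. The size of the shift is 0.13, 0.08 and 0.05 cohort SD for r = 0.5, 0.7 and 0.8.

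**5. Simulation without truncation, 30 v 100, equal slopes.** Both estimators were unbiased on average. The slope of the change estimate on the imbalance was −0.50, −0.32 and −0.20 for r = 0.5, 0.7 and 0.8. For the adjusted estimate it was within 0.02 of zero.

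**The case against.** The strongest reply is that the analysis is exploratory, in a pilot whose first objective is feasibility and acceptability. The plan does not list the GEE covariates, so the absence of adjustment is read from silence. Every gain depends on an assumed r. All of this stands, and it limits the weight of the point. It does not remove it: the text defines the contrast as one of change, and that is what an analyst would fit.

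A reader might also infer more than the documents support:

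- **That all five measures could be adjusted with no new data.** No control baseline or follow-up is described for SART, Tower of London or DEX. For those three, missing control data come before any choice of adjustment.
- **That the other measures gain much more.** Without truncation the ratio is (1 + r)/2 = 0.75, 0.85, 0.90, or 11% to 33% more people. At best this concerns PDQ. Entry requires subjective cognitive complaints, so a self-report score may be range-restricted too.
- **That the change contrast is biased.** Under random selection it is unbiased on average. The shift is conditional on the sample drawn, and its variability is already in the confidence interval, so lost precision and imbalance are partly one phenomenon.
- **That adjustment can never lose precision.** At 30:100 a common-slope model has no such guarantee if slopes differ by group. In simulation without truncation, assumed slopes (GMT/control) of 0.8/0.6 gave a variance ratio of 0.91, 0.9/0.6 gave 1.00, and 0.9/0.4 gave 1.07. Different slopes are conceivable: GMT participants are retested within 4 weeks of a 9-week programme, while cohort visits are 9 months apart.
- **That the analysis misses a power it claims for one outcome.** The 80% is stated for all measures together. No single-outcome power is claimed.

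Finally, GMT participants consent to the sub-study, and the handling of people who are selected but decline is not stated. Imbalance may then not be chance alone. Neither estimator is guaranteed unbiased in that case.

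**Conclusion.** The point holds for B-CAM, and plausibly for PDQ. The exploratory between-group analysis gives up some precision by contrasting change when the baseline of the primary cognitive outcome is known in both groups. The precision gain is small, a few points of power on B-CAM alone. The protection against a two-SE baseline imbalance is of similarly modest size. These figures rest on the assumed r, normality, a cut at the cohort median, random selection and similar baseline slopes in the two groups. Severity is optional to modest.

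**What to change.** In *Analysis and Sample Size*, specify that the between-group model takes the follow-up score as outcome, with group and the baseline value of that measure as terms. Apply this to B-CAM, and to any other measure that has a baseline in both groups. In a pooled GEE, let the baseline coefficient differ by measure. Keep the change contrast as a sensitivity analysis, so that a disagreement between the two would show.

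State which measures have baseline and follow-up data in the control group. The fix does not extend to SART, Tower of London or DEX unless controls have those data.

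The cost is one or two sentences of analysis wording and one more model term per measure. For B-CAM no new baseline data are needed. The downside is reliance on similar baseline slopes in the two groups.

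### The exploratory between-group B-CAM comparison contrasts raw change and leaves unused the earlier B-CAM scores the cohort should hold; adding them is a cheap precision gain of uncertain size, not the repair of an error

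*Combined protocol and SAP*

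**What the plan says.** Under Analysis and Sample Size, the controlled comparison is "a between group comparison contrasting change in cognitive outcomes between the GMT group and the concurrent control group assessed in the main study", labelled exploratory. The same section says that, for all analyses, "the B-CAM (performance measure) will be the primary cognitive outcome". The model is a GEE for continuous outcomes over five measures rescaled to 0–100, with 30 GMT participants and 100 controls. No baseline covariate or earlier cohort score is named.

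Four other statements bear on whether earlier scores exist:

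- Study Design names B-CAM as the cohort's primary outcome and says participants are "followed every 9 months for 27 months".
- The same section says the cohort "is enrolling consecutive patients attending 5 HIV clinics across Canada", so some people may be at their first visit.
- Procedure: "Participants will be recruited at the time of their routine +BHN study visit". It does not say which visit in the sequence.
- Subject Identification Number Assignment: "Subject Identification (ID) numbers assigned for the core platform will be used for this sub-study".

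Eligibility requires "performance on objective computerized cognitive tests that falls at or below the 50th percentile of performance in the cohort as a whole". The Protocol Summary gives a B-CAM cut-off of 24 instead. Neither place says which visit's score is used.

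**The concern.** Each person is reduced to one pre and one post score. For B-CAM, anyone past a first cohort visit should have at least one earlier score, in either group, recorded before GMT selection and linkable by ID. Such a score carries information about the person's underlying level that a single noisy entry score does not.

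The usual remedy for a raw change contrast is to adjust for the entry score. It is weaker than usual here if that score was also the eligibility score, because its range has then been cut at about the median.

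At stake is the precision of the only controlled comparison in the plan. The hypothesis and the second objective in the Protocol Summary are framed against a wait-list group. For B-CAM alone, 30 v 100 gives a little under 50% power at 0.4 SD.

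**Working it through.** **Plan's own figure.** The plan states 80% power at 0.4 SD after multiplying the sample by 1.8. That is 54 v 180, and two-sided 5% power is 73% (one-sided 82%); the two-sided detectable effect is 0.435 SD. The 80% does not reproduce two-sided. That is a separate matter, and nothing below depends on it. For B-CAM alone, 30 v 100 at 0.4 SD gives 48% (t test, two-sided 5%).

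**Assumptions (none is in the documents).** Scores are normal with SD 1 in the cohort. The correlation r between any two visits is equal, 0.6–0.8. Eligibility is set at the median of the entry score. The only correlation the plan gives, 0.2, is between measures, not visits.

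**Formulas.** A median cut leaves the entry score with variance 1 − 2/π = 0.363.

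- Raw change: (1 − r)² × 0.363 + (1 − r²)
- Post given entry: 1 − r²
- Post given entry and previous: 1 − 2r²/(1 + r)

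At r = 0.7: 0.09 × 0.363 + 0.51 = 0.543; then 0.510; then 1 − 0.98/1.7 = 0.424.

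| r | Raw change | Entry | Entry + previous | Entry removes | Previous removes, of the remainder | Total |
|---|---|---|---|---|---|---|
| 0.6 | 0.698 | 0.640 | 0.550 | 8% | 14% | 21% |
| 0.7 | 0.543 | 0.510 | 0.424 | 6% | 17% | 22% |
| 0.8 | 0.375 | 0.360 | 0.289 | 4% | 20% | 23% |

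Simulation agrees with these values.

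**Power at r = 0.7.** The effect is 0.4 SD of the change score, so the adjusted effect size is 0.4 × √(raw change variance / residual variance).

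- Raw change: 0.400, power 48%
- Entry: 0.4 × √(0.543/0.510) = 0.413, power 50%
- Entry + previous: 0.4 × √(0.543/0.424) = 0.453, power 58%

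**Relaxing the assumptions (r = 0.6 / 0.7 / 0.8).**

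- *Eligibility set on the previous score.* The further gain is about 7 / 10 / 13% by simulation. The entry score then does more of the work, and the total against raw change is 31 / 29 / 28%.
- *Half the people without an earlier score.* With mean fill and an indicator, simulation gives 6.4 / 7.2 / 7.5%, and power of about 53% at r = 0.7. This is a little under half of 14–20% because one entry slope is shared by people with and without an earlier score.
- *Correlation decaying with time.* If the previous-to-post correlation is c, the further gain is ((c − r²)/(1 − r²))². Halfway between equal correlation and AR(1), c = 0.48 / 0.595 / 0.72 and the gain is 3.5 / 4.2 / 4.9% (power about 52% at r = 0.7). Under AR(1), c = r² and the gain is zero (power stays at 50%).

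**Does the median cut create the 14–20%?** No. Under equal correlation the further gain is r²/(1 + r)², and simulation gives the same value with and without the cut on the entry score (16.7% v 16.8% at r = 0.7). The cut weakens entry-score adjustment relative to raw change: without it the gain would be (1 − r)/2 = 20 / 15 / 10%, against 8 / 6 / 4% with it.

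**The case against.** The strongest reply is that a change-score contrast is valid without a second baseline, that the comparison is labelled exploratory in a pilot whose first objective is feasibility, and that no protocol decision turns on 48% against 58% power. All of that stands. It makes this an optional improvement.

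The size is also open to challenge. Equal correlation drives the 14–20%, yet the spacing differs: the GMT post test falls within 4 weeks of a 9-week programme, while the previous cohort visit is 9 months before entry. Decay is plausible, and the gain could be small. A gain of exactly zero, however, needs observed scores to follow AR(1), which leaves no room for measurement error in a brief test. The Background also describes mild impairment as largely static. Neither point fixes a value.

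A reader might infer more than the documents support:

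- *That the entry score explains little.* After the cut it still explains 17–39% of post-score variance at r = 0.6–0.8. It adds little only relative to a change score, which already uses it.
- *That the previous score played no part in selection.* The documents do not say which visit's score set eligibility.
- *That everyone has an earlier score.* The cohort is still enrolling.
- *That all five outcomes gain.* SART, Tower of London and DEX are sub-study tests with no earlier cohort scores described. The effect on the pooled five-measure estimate was not calculated and would be smaller.

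**Conclusion.** The omission is real. The plan contrasts raw B-CAM change although earlier scores should exist, under the same IDs, for people recruited after a first +BHN visit. Because GMT participants are to be drawn at random from those eligible and the earlier score precedes that draw, adjusting for it should not bias the contrast.

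The gain is conditional. The favourable case (equal correlations of 0.6–0.8, eligibility on the entry score, everyone with an earlier score) is about 21–23% less variance than raw change. The previous score's share of that may be far smaller, and nil under AR(1) decay. It would be wrong to read 14–20% as a property of this trial, as a share of total variance, or as a consequence of the median cut. This is a low-cost improvement to an exploratory comparison.

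**What to change.** In Analysis and Sample Size, prespecify for the between-group B-CAM analysis a model of the post score on group, entry-visit B-CAM and previous-visit B-CAM. For people without an earlier score, set it to the mean and add a missing indicator. State which visit's score determines eligibility and, once known, how many people in each group have an earlier score.

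Do not use the earlier score as a second baseline in the uncontrolled pre–post mean, where practice between cohort visits would be counted as change. Treat PDQ in the same way if the cohort collects it at each visit. Leave SART, Tower of London and DEX as planned.

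The cost is a sentence or two of SAP text, one variable from the cohort database, and one or two model terms beyond the entry score, which is negligible with 130 people. It should be written before outcomes are seen, so that it is not a post hoc choice of covariate.
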